[figure not shown]

**Document History**

Document	Version Date	Summary of Changes
Original Protocol	08 April 2016	Not applicable (N/A)

## PROTOCOL SUMMARY

### Background

This study is an open-label extension (OLE) to Protocol B5161002 and will provide an assessment of the long term safety, efficacy, pharmacodynamics (PD) and pharmacokinetics (PK) of intravenous (IV) dosing of PF-06252616 in boys with Duchenne muscular dystrophy (DMD).

### Objectives and Endpoints

#### Objectives

- To evaluate the long-term safety of IV dosing of PF-06252616 in boys with DMD.
- To evaluate the long-term efficacy of PF-06252616 using functional assessments and strength.
- To assess the PK and immunogenicity of PF-06252616.
- To evaluate PD markers that may be informative in demonstrating the pharmacologic effect of PF-06252616.
- To evaluate the long-term functional health effects of PF-06252616 on Pediatric Outcomes Data Collection Instrument (PODCI) Parent-report and Adolescent self-report scores.
- To assess the long-term effects of PF-06252616 on health-related quality of life (HRQL) and healthcare resource utilization (HRU) in boys with DMD.
- To evaluate the long-term effects of PF-06252616 on caregiver burden, HRQL and work productivity and activity impairment.
- To collect exploratory biomarker samples for biobanking.

#### Endpoints

- Safety:
  - Incidence and/or rate of intolerance or dose limiting treatment related adverse events (AEs).
  - Incidence and/or rate, severity and causal relationship of treatment emergent adverse events (TEAEs) and withdrawals due to TEAEs.
  - Incidence and magnitude of abnormal laboratory findings.
  - Abnormal and clinically relevant changes in liver magnetic resonance imaging (MRI) and physical examinations.

- Efficacy:
  - Baseline values and change from baseline in the following functional assessment tests; Pulmonary function test (PFTs) (to include forced vital capacity [FVC], forced expiratory volume in 1 second [FEV1] and peak expiratory flow rate [PEFR]), 4 Stair Climb (4SC), Northstar Ambulatory Assessment (NSAA), Performance of Upper Limb (PUL), Range of motion (ROM) and 6 minute walk distance (6MWD).
  - Mean change from baseline in muscle strength measured by myometry.
- PK and Immunogenicity:
  - Trough serum PF-06252616 concentrations for all subjects receiving active drug.
  - Incidence of anti-drug antibody (ADA) and neutralizing antibody (NAb).
- PD:
  - Change from baseline of Lean Body Mass (LBM) determined via whole body dual image x-ray absorptiometry (DXA).

### **Clinical Outcome Assessments (COA)**

- Change from baseline in the Pediatric Outcomes Data Collection Instrument (PODCI) Parent-report and Adolescent self-report scores.
- Change from baseline in the EuroQol 5 Dimensions 3 Levels (EQ-5D-3L) Health Questionnaire.
- Change from baseline in the EuroQol 5 Dimensions - Youth (EQ-5D-Y) Health Questionnaire.
- Change from baseline in the Healthcare Resource Utilization (HRU) questionnaire.
- Change from baseline in Zarit Burden Interview (ZBI).
- Change from baseline in the Work Productivity and Activity Impairment Questionnaire adapted for caregiving (WPAI:CG) in the percent work time missed, percent impairment while working, percent overall work impairment, and percent activity impairment due to a child's Duchenne muscular dystrophy.

### **Study Design**

Approximately 105 eligible subjects will be assigned to receive an individualized maximum tolerated dose based on their tolerability profile/data from B5161002. No placebo comparator will be assessed. Consenting subjects who complete the B5161002 study will be

invited to transition directly to the OLE study. Subjects' results from the B5161002 study may be used as screening data for the current study.

### **Study Treatments**

The individual dose level selected for each subject will be based on the maximum tolerated dose from the parent Study B5161002. Subjects will be dosed with one of three PF-06252616 dose levels: 5 mg/kg, 20 mg/kg or 40 mg/kg.

### **Statistical Methods**

#### **Safety Analysis**

Summary statistics will be performed on the following safety endpoints:

- Incidence and/or rate of intolerance or dose limiting treatment related AEs.
- Incidence and/or rate, severity and causal relationship of TEAEs and withdrawals due to TEAEs.
- Incidence and magnitude of abnormal laboratory findings.
- Abnormal and clinically relevant changes in liver MRI and physical examinations.

#### **Analysis of efficacy and PD endpoints**

Baseline values, change from baseline to last visit in PFTs, 4SC, NSAA, PUL, 6MWD, muscle strength by myometry and lean body mass by DXA will be described based on summary statistics including minimum, median, mean, maximum, and standard deviation. Change from baseline may also be assessed for any or all intermediate visits.

#### **Analysis of PK and Immunogenicity**

- Summary statistics will be provided for trough serum concentrations by dose.
- Incidence of ADA and NAb.

#### **Analysis of Clinical Outcomes Assessments (Caregiver and patient-reported)**

Summary statistics will be presented for the PODCI, EQ-5D-Y, EQ-5D-3L, Zarit Burden Interview, WPAI-CG, and HRU by baseline, treatment and time point as applicable. Methodology for any treatment group comparisons will be specified in the statistical analysis plan (SAP).

## SCHEDULE OF ACTIVITIES

The Schedule of Activities tables provide an overview of the protocol visits and procedures for Year 1, Years 2-4 and Early Withdrawal. In order to accommodate the scheduling, assessments may be conducted on separate days within the visit window. Refer to the Procedures and Assessments sections of the protocol for detailed information on each procedure and assessment required for compliance with the protocol.

The investigator may schedule visits (unplanned visits) in addition to those listed on the schedule of activities, in order to conduct evaluations or assessments required to protect the wellbeing of the subject.

### Study Flowchart: Year 1

Year 1														
Visit Number a	Screen a	1	2	3	4	5	6	7	8	9	10	11	12	13
Study Week a		1	5	9	13	17	21	25	29	33	37	41	45	49
Study Day a		1	29	57	85	113	141	169	197	225	253	281	309	337
Visit Window a	Up to 42 days								± 3 days					
Entry/Safety Assessments/Questionnaire														
Informed consent/Assent b	X													
Demography	X a													
Medical History	X a													
Medication History	X													
Inclusion/Exclusion Review	X	X												
Physical Examination c	X a				X			X			X			X
Tanner Stage and Testicular Volume d	X a													X
Height e	X a								X					X
Weight f	X a	→	→	→	→	→	→	→	→	→	→	→	→	→
Vital Signs g	X a	X			X			X			X			X
Single ECG	X a							X						X
Cardiac MRI (or Echocardiogram) h	X a													X

PF-06252616

B5161004

Final Protocol, 08 April 2016

090177e1911f2727\Approved\Approved On: 18-Jun-2019 06:41 (GMT)

Year 1														
Visit Number a	Screen a	1	2	3	4	5	6	7	8	9	10	11	12	13
Study Week a		1	5	9	13	17	21	25	29	33	37	41	45	49
Study Day a		1	29	57	85	113	141	169	197	225	253	281	309	337
Visit Window a	Up to 42 days								± 3 days					
Clinical Laboratory Tests i	X a				X			X			X			X
Serum Ferritin, Serum Iron, TIBC, % Transferrin Saturation i	X a				X			X			X			X
Hormones (LH, FSH, T4, TSH, androstenedione, testosterone) e	X a													X
Fecal Occult Blood d	X a				X			X			X			X
Clinical Outcomes Assessments (Completed by Caregiver)														
PODCI Questionnaire k	X a				X			X						X
C-SSRS L	X a				X			X			X			X
EQ-5D-3L	X m				X			X						X
HRU	X m				X			X						X
ZBI	X m				X			X						X
WPAI-CG	X m				X			X						X
Clinical Outcomes Assessments (Completed by Subject)														
PODCI Questionnaire	X m,n				X			X						X
EQ-5D-Y	X m				X			X						X
Imaging Assessments														
MRI-Liver	X a							X						X
DXA-Spine	X a													X
DXA-Whole Body	X a													X
X-ray (hand and wrist) d	X a													X
Functional Assessments														
Ambulatory Status o	X	→	→	→	→	→	→	→	→	→	→	→	→	X
PFTs	X					X			X					X
4 Stair Climb p	X a				X			X						X

PF-06252616

B5161004

Final Protocol, 08 April 2016

Year 1														
Visit Number a	Screen a	1	2	3	4	5	6	7	8	9	10	11	12	13
Study Week a		1	5	9	13	17	21	25	29	33	37	41	45	49
Study Day a		1	29	57	85	113	141	169	197	225	253	281	309	337
Visit Window a	Up to 42 days								± 3 days					
Northstar Ambulatory Assessment p	X a				X			X						X
Range of Motion	X a				X			X						X
Strength Assessment	X a				X			X						X
PUL	X a				X			X						X
6MWT p	X a				X			X						X
Investigational Product Administration														
Investigational Product administration q		X	X	X	X	X	X	X	X	X	X	X	X	X
PK/PD, Immunogenicity and Biobanking														
PK sample r	X a							X						X
Immunogenicity	X a							X						X
Group 1 and Group 2 Biomarkers	X													X
Infusion Site Reaction monitoring		X	→	→	→	→	→	→	→	→	→	→	→	X
Adverse event monitoring		X	→	→	→	→	→	→	→	→	→	→	→	X
Concomitant medication	X	→	→	→	→	→	→	→	→	→	→	→	→	X

Abbreviations: → = ongoing/continuous monitoring; 6MWT=Six minute walk test; C-SSRS=Columbia Suicide Severity Rating Scale, DXA=Dual-energy x-ray absorptiometry; ECG =electrocardiogram; EQ-5D-3L=EuroQoL 5 Dimensions 3 Levels; EQ-5D-Y=EuroQoL 5 Dimensions - Youth; FSH=Follicle stimulating hormone; HRU=Healthcare Resource Utilization; LH=Luteinizing hormone; MRI=magnetic resonance image; PD=Pharmacodynamics; PFTs =pulmonary function tests; PK=Pharmacokinetics, PODCI=Pediatric Outcomes Data Collection Instrument; PUL=Performance of Upper Limb, T4=thyroxine; TIBC=Total iron binding capacity, TSH=thyroid stimulating hormone; WPAI-CG=Work Productivity and Activity Impairment questionnaire adapted for Caregiving; ZBI=Zarit Burden Interview.

- Subjects will enroll in the study within 42 days of completion of the Week 97 of the parent study B5161002. If this window is exceeded, the sponsor and investigator will assess if the subject may still participate in this OLE study, and which, if any assessments must be completed to confirm eligibility. If needed assessments may be performed on consecutive days within the study visit window. For example where functional assessments and imaging assessments are collected at the same visit, subjects can be assessed over a 2 day period. Demography and medical history will be collected from Study B5161002. The following assessments may be collected as screening data from subject's Week 97 visit within Study B5161002. These include: Physical

Year 1														
Visit Number a	Screen a	1	2	3	4	5	6	7	8	9	10	11	12	13
Study Week a		1	5	9	13	17	21	25	29	33	37	41	45	49
Study Day a		1	29	57	85	113	141	169	197	225	253	281	309	337
Visit Window a	Up to 42 days								± 3 days					

Examination, Tanner Stage and Testicular Volume, Height, Weight, Vital Signs, Single ECG, Cardiac MRI (or Echocardiogram), Clinical Laboratory Tests, GLDH, Serum Ferritin, Serum Iron, TIBC%, Transferrin Saturation, Hormones (LH, FSH, T4, TSH, andostenedione, testosterone), Fecal Occult Blood, PODCI, C-SSRS, MRI-Liver (data from Week 93), DXA-Spine, DXA-Whole Body, X-ray (hand and wrist), Functional Assessments (not including ambulatory status which is not collected in B5161002), PK, Immunogenicity.

- b. Informed consent must be provided by the subject's caregiver (parent or legal guardian). Subject will be required to provide assent in compliance with local regulations and IRB/EC requirements.
- c. The physical examination will also include a nose and throat mucosal exam.
- d. Once sexual maturity is reached defined as Tanner Stage V, Tanner stage and Testicular Volume, x-ray (hand and wrist) and hormone testing are no longer mandatory.
- e. Height and hormone testing should be performed in the morning. If a subject is unable to stand safely, an estimated height can be calculated using the subject's ulnar length and the instructions provided in the functional assessment manual.
- f. Weight will be collected at each visit. The weight from the current visit or the previous month's visit can be used to calculate the appropriate dose by body weight.
- g. Vital sign evaluations will include pre-dose supine blood pressure, pulse rate, respiratory rate and temperature.
- h. Cardiac MRI is the preferred method of imaging, If it is not possible to perform cardiac MRI (eg, not available at the site) echocardiogram will be acceptable. The same method of cardiac imaging utilized in B5161002 should be used consistently within a single subject through Study B5161004. Cardiac MRI with gadolinium should only be performed after all other imaging assessments are completed.
- i. Clinical laboratory tests include hematology, chemistry, gamma-glutamyl transferase (GGT), glutamate dehydrogenase (GLDH), prothrombin time (PT), activated partial thromboplastin time (aPTT), creatine kinase, amylase, and urinalysis. In Year 1, cardiac troponin I will be collected at Screening, Week 49 and Early Withdrawal only.
- j. If a Week 97 B5161002 stool sample result is not available at the screening visit, a collection kit and mailing supplies will be sent home and the caregiver will be responsible for collection and mailing the sample back to the site. For all other visits after screening, a stool sample will be collected at home within approximately 1 week prior to the scheduled visit.
- k. PODCI Completed by Parent/Caregiver.
- l. For the C-SSRS the "Children's Since Last Visit" assessment will be performed. This will be completed by the caregiver.
- m. The PODCI Adolescent self-report, EQ-5D-Y, EQ-5D-3L, ZBI, and HRU questionnaires are new assessments not included in the parent study B5161002 and should be collected at screening and all subsequent visits outlined in the [Schedule of Activities](#). If a subject is unwilling to provide self-reported data

Year 1														
Visit Number a	Screen a	1	2	3	4	5	6	7	8	9	10	11	12	13
Study Week a		1	5	9	13	17	21	25	29	33	37	41	45	49
Study Day a		1	29	57	85	113	141	169	197	225	253	281	309	337
Visit Window a	Up to 42 days								± 3 days					

they can still participate in the study.

- n. Children will become eligible to complete the Adolescent self-report version of the PODCI when they turn 11 years of age at which time they should be asked to complete the PODCI Adolescent self-report version at indicated time points throughout the study. In addition, caregivers will continue to complete the PODCI Parent-report (2-10 years) version throughout the study. If a subject is unwilling to provide self-reported data they can still participate in the study.
- o. Ambulatory status will be recorded at the screening visit. Ambulation is defined as the ability to walk unassisted and without braces for at least 10 m. At subsequent visits if subject becomes non-ambulatory this should be recorded.
- p. If a loss of ambulation has occurred 4 Stair Climb, Northstar Ambulatory Assessment and 6MWT do not need to be completed. Please record date that ambulation was lost.
- q. Investigational product should be delivered in a 2 hour window ±30 minutes including the flush time. If a dosing visit cannot be conducted within the visit window, attempts should be made to bring the subject back for dosing as soon as possible; however the dosing **must not occur** within 2 weeks prior to the next scheduled dose. If the subject cannot return in this timeframe, the dose should be missed and the next visit should be conducted per the [Schedule of Activities](#).
- r. PK samples to be taken prior to dosing.

PF-06252616

B5161004

Final Protocol, 08 April 2016

**Study Flowchart: Year 2, 3 and 4 and Early Withdrawal**

	Year 2,3,4 and Early Withdrawal													Early Withdrawal
	14 26, 38	15, 27, 39	16 28, 40	17, 29, 41	18, 30, 42	19, 31, 43	20, 32, 44	21, 33, 45	22, 34, 46	23, 35, 47	24, 36, 48	25, 37, 49		
Visit Number a	14 26, 38	15, 27, 39	16 28, 40	17, 29, 41	18, 30, 42	19, 31, 43	20, 32, 44	21, 33, 45	22, 34, 46	23, 35, 47	24, 36, 48	25, 37, 49		
Study Week a	53, 101, 149	57, 105, 153	61, 109, 157	65, 113, 161	69 117, 165	73 121, 169	77 125, 173	81 129, 177	85 133, 181	89 137, 185	93 141, 189	97 145, 193		
Study Day a	365, 701, 1037	393, 729, 1065	421, 757, 1093	449, 785, 1121	477, 813, 1149	505 841, 1177	533, 869, 1205	561, 897, 1233	589, 925, 1261	617, 953, 1289	645, 981, 1317	673, 1009, 1345		
Visit Window	± 3 days													
Safety Assessments/Questionnaire														
Physical Examination b			X			X			X			X		X
Tanner Stage and Testicular Volume c						X							X	X
Height d						X							X	X
Weight e	X	→	→	→	→	→	→	→	→	→	→	→	X	X
Vital Signs f				X		X			X				X	X
Single ECG			X			X			X				X	X
Cardiac MRI (or Echocardiogram) g													X	X
Clinical Laboratory Tests h			X			X			X				X	X
Serum Ferritin, Serum Iron, TIBC, % Transferrin Saturation h			X			X			X				X	X
Hormones (LH, FSH, T4, TSH, androstenedione, testosterone) c,d						X							X	X
Fecal Occult Blood i			X			X			X				X	X
Clinical Outcomes Assessments (Completed by Caregiver)														
PODCI Questionnaire j							X						X	X
C-SSRS k						X			X				X	X
EQ-5D-3L						X							X	X
HRU						X							X	
ZBI						X							X	X
WPAI-CG						X							X	X
Clinical Outcomes Assessments (Completed by Subject)														
PODCI Questionnaire l	X					X							X	X
EQ-5D-Y	X					X							X	X
Imaging Assessments														

PF-06252616

B5161004

Final Protocol, 08 April 2016

090177e1911f2727\Approved\Approved On: 18-Jun-2019 06:41 (GMT)

Visit Number a	Year 2,3,4 and Early Withdrawal												
	14 26, 38	15, 27, 39	16 28, 40	17, 29, 41	18, 30, 42	19, 31, 43	20, 32, 44	21, 33, 45	22, 34, 46	23, 35, 47	24, 36, 48	25, 37, 49	Early Withdrawal
Study Week a	53, 101, 149	57, 105, 153	61, 109, 157	65, 113, 161	69 117, 165	73, 121, 169	77, 125, 173	81, 129, 177	85, 133, 181	89, 137, 185	93, 141, 189	97, 145, 193	
Study Day a	365, 701, 1037	393, 729, 1065	421, 757, 1093	449, 785, 1121	477, 813, 1149	505, 841, 1177	533, 869, 1205	561, 897, 1233	589, 925, 1261	617, 953, 1289	645, 981, 1317	673, 1009, 1345	
Visit Window	± 3 days												
MRI-Liver						X						X	X
DXA-Spine												X	X
DXA-Whole Body												X	X
X-ray (hand and wrist) c												X	X
Functional Assessments													
Ambulatory status m	X	→	→	→	→	→	→	→	→	→	→	X	X
PFTs						X						X	X
4 Stair Climb n					X							X	X
Northstar Ambulatory Assessment n					X							X	X
Range of Motion					X							X	X
Strength Assessment					X							X	X
PUL					X							X	X
6MWT n					X							X	X
Investigational Product Administration													
Investigational Product administration o	X	X	X	X	X	X	X	X	X	X	X		
PK/Immunogenicity													
PK sample p						X						X	X
Immunogenicity					X							X	X
Biobanking Sample (Group 1 and Group 2 Biomarkers)												X	
Infusion Site Reaction monitoring	X	→	→	→	→	→	→	→	→	→	→	→	X
Adverse event monitoring	X	→	→	→	→	→	→	→	→	→	→	→	X
Concomitant medication	X	→	→	→	→	→	→	→	→	→	→	→	X

Abbreviations: → = ongoing/continuous monitoring; 6MWT=Six minute walk test; C-SSRS=Columbia Suicide Severity Rating Scale, DXA=Dual-energy x-ray absorptiometry; ECG = electrocardiogram; EQ-5D-3L=EuroQoL 5 Dimensions 3 Levels; EQ-5D-Y=EuroQoL 5 Dimensions - Youth; FSH= Follicle stimulating hormone; HRU=Healthcare Resource Utilization; LH= Luteinizing hormone; MRI=magnetic resonance image; PD=Pharmacodynamics; PFTs = pulmonary function tests; PK=Pharmacokinetics, PODCI=Pediatric Outcomes Data Collection Instrument; PUL=Performance of Upper Limb, T4 =thyroxine; TIBC=Total

Visit Number a	Year 2,3,4 and Early Withdrawal												
	14 26, 38	15, 27, 39	16 28, 40	17, 29, 41	18, 30, 42	19, 31, 43	20, 32, 44	21, 33, 45	22, 34, 46	23, 35, 47	24, 36, 48	25, 37, 49	Early Withdrawal
Study Week a	53, 101, 149	57, 105, 153	61, 109, 157	65, 113, 161	69 117, 165	73, 121, 169	77, 125, 173	81, 129, 177	85, 133, 181	89, 137, 185	93, 141, 189	97, 145, 193	
Study Day a	365, 701, 1037	393, 729, 1065	421, 757, 1093	449, 785, 1121	477, 813, 1149	505, 841, 1177	533, 869, 1205	561, 897, 1233	589, 925, 1261	617, 953, 1289	645, 981, 1317	673, 1009, 1345	
Visit Window	± 3 days												

iron binding capacity, TSH=thyroid stimulating hormone; WPAI-CG=Work Productivity and Activity Impairment questionnaire adapted for Caregiving; ZBI=Zarit Burden Interview.

- a. If needed assessments may be performed on consecutive days within the study visit window. For example where functional assessments and imaging assessments are collected at the same visit, subjects can be assessed over a 2 day period.
- b. The physical examination will also include a nose and throat mucosal exam.
- c. Once sexual maturity is reached defined as Tanner Stage V, Tanner stage and Testicular Volume, x-ray (hand and wrist) are no longer mandatory.
- d. Height and hormone testing should be performed in the morning.
- e. Weight will be collected at each visit. The weight from the current visit or the previous month's visit can be used to calculate the appropriate dose by body weight.
- f. Vital sign evaluations will include pre-dose supine blood pressure, pulse rate, respiratory rate and oral temperature.
- g. Cardiac MRI is the preferred method of imaging. If it is not possible to perform cardiac MRI (eg, not available at the site) echocardiogram will be acceptable. The same method of cardiac imaging utilized in B5161002 should be used consistently within a single subject through Study B5161004. Cardiac MRI with gadolinium should only be performed after all other imaging assessments are completed
- h. Clinical laboratory tests include hematology, chemistry, gamma-glutamyl transferase (GGT), glutamate dehydrogenase (GLDH), prothrombin time (PT), activated partial thromboplastin time (aPTT), creatine kinase, amylase, and urinalysis. Cardiac troponin I will be collected at Week 97, 145, 193 and Early Withdrawal.
- i. A stool sample will be collected at home within approximately 1 week prior to the scheduled visit.
- j. PODCI Completed by Parent/Caregiver.
- k. For the C-SSRS the "Children's Since Last Visit" assessment will be performed. This will be completed by the caregiver.
- l. The PODCI Adolescent self-report if applicable. Children will become eligible to complete the Adolescent self-report version of the PODCI when they turn 11 years of age at which time they should be asked to complete the PODCI Adolescent self-report version at indicated time points throughout the study. In addition, caregivers will continue to complete the PODCI Parent-report (2-10 years) version throughout the study. If a subject is unwilling to provide self-

Visit Number a	Year 2,3,4 and Early Withdrawal												Early Withdrawal
	14 26, 38	15, 27, 39	16, 28, 40	17, 29, 41	18, 30, 42	19, 31, 43	20, 32, 44	21, 33, 45	22, 34, 46	23, 35, 47	24, 36, 48	25, 37, 49	
Study Week a	53, 101, 149	57, 105, 153	61, 109, 157	65, 113, 161	69 117, 165	73, 121, 169	77, 125, 173	81, 129, 177	85, 133, 181	89, 137, 185	93, 141, 189	97, 145, 193	
Study Day a	365, 701, 1037	393, 729, 1065	421, 757, 1093	449, 785, 1121	477, 813, 1149	505, 841, 1177	533, 869, 1205	561, 897, 1233	589, 925, 1261	617, 953, 1289	645, 981, 1317	673, 1009, 1345	
Visit Window	± 3 days												

reported data they can still participate in the study.

- m. Ambulatory status should be reviewed at each visit. Ambulation is defined as the ability to walk unassisted and without braces for at least 10 m. If a subject becomes non-ambulatory this should be recorded in the CRF.
- n. If a loss of ambulation has occurred 4 Stair Climb, Northstar Ambulatory Assessment and 6MWT do not need to be completed. Please record date that ambulation was lost.
- o. Investigational product should be delivered in a 2 hour window ±15 minutes including the flush time. If a dosing visit cannot be conducted within the visit window, attempts should be made to bring the subject back for dosing as soon as possible; however the dosing **must not occur** within 2 weeks prior to the next scheduled dose. If the subject cannot return in this timeframe, the dose should be missed and the next visit should be conducted per the [Schedule of Activities](#).
- p. PK samples to be taken prior to dosing.

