#### **1.4. Rationale for Dosage Selection and Method of Administration**

The dose for each subject will be based on their individual maximum tolerated dose (MTD) up to 40 mg/kg from Study B5161002. This study will use the same route and frequency of administration as Study B5161002. IV was chosen as the route of administration for B5161002 to support the large dose that will be required to obtain the targeted GDF-8 coverage. The frequency of administration was chosen as 4 weeks to achieve targeted GDF-8 coverage but also to reduce the burden on subject travel to study sites.

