#### **3.2. Duration of Study and Subject Participation**

The OLE study is planned to be conducted over a period of 4 years. The end of the study will be the last visit of the last subject for purposes of closing out sites, informing the institutional review board/ethics committee (IRB/EC), and ceasing to send Council for International Organizations of Medical Sciences (CIOMS) reports.

Depending on when subjects begin the OLE study, their participation may be as long as 4 years. Subjects may be withdrawn from the OLE study should the parent study, B5161002 fail to meet its planned study objectives, is terminated early for other reasons (eg, sponsor decision) or the drug is commercialized.

Subjects will be administered monthly infusions of study drug as well as completion of safety and efficacy assessments as per the [Schedule of Activities](#).

In the case where subjects are traveling from a distance, local overnight accommodation will be offered.

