#### **5. STUDY TREATMENTS**

For the purposes of this study, and per International Conference on Harmonization (ICH) guidelines, investigational product is defined as a pharmaceutical form of an active ingredient being tested or used as a reference in a clinical trial, including a product with a marketing authorization when used or assembled (formulated or packaged) in a way different from the approved form, or when used for an unapproved indication, or when used to gain further information about an approved use (ICH E6 1.33).

PF-06252616 is incompatible with sodium chloride containing solutions. Therefore, do not use Normal Saline (0.9% sodium chloride) or other sodium chloride containing solutions, as

a diluent or for flushing the infusion line. Dextrose 5% solution is recommended for use during flushing to ensure complete delivery of the prepared dosing solution.

Subjects will be administered PF-06252616 by IV infusion. The investigator site will maintain the high level oversight of all subject IV infusions if an alternative infusion location is used by the site. Once the investigational product is determined to be tolerated by the subject, the investigator and sponsor may explore the possibility of alternative infusion locations, as appropriate. Additional administration instructions will be provided to facilitate the infusion of this investigational product at alternative infusion locations.

This is an open-label study. Subjects will receive monthly doses of either, 5 mg/kg, 20 mg/kg or 40 mg/kg following confirmation of their MTD from the parent study B5161002. Dose levels may be adjusted based on emerging safety or efficacy data from B5161002.

Subjects should be administered the investigational product within the visit window according to the [Schedule of Activities](#). If a dosing visit cannot be conducted within the visit window, attempts should be made to bring the subject back for dosing as soon as possible; however the dosing must not occur within 2 weeks prior to the next scheduled dose. If the subject cannot return for dosing in this timeframe, the dose should be missed and the next visit should be conducted per the [Schedule of Activities](#).

Please refer to the dosage and administration instructions in the Investigational Product Manual and the Administration Card for complete information on storage, stability, preparation and administration of PF-06252616.

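### The Year 2-4 flowchart marks no study drug in the column shared by Weeks 97, 145 and 193, so two mid-study doses drop out against the 4-weekly regimen in the text (minor inconsistency, subject to checking the source table)

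*Protocol*

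**What the plan says.** The regimen is stated three times in the text, each time without an exception for annual visits.

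- Section 1.4: "This study will use the same route and frequency of administration as Study B5161002". It adds: "The frequency of administration was chosen as 4 weeks to achieve targeted GDF-8 coverage". Section 1.3 gives the parent study's interval as every 4 weeks.
- Section 3.2: "Subjects will be administered monthly infusions of study drug".
- Section 5: "Subjects will receive monthly doses of either, 5 mg/kg, 20 mg/kg or 40 mg/kg following confirmation of their MTD".

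Section 5 also makes the Schedule of Activities the operative timetable: "Subjects should be administered the investigational product within the visit window according to the" Schedule.

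The Schedule has two flowcharts. In Year 1 the row "Investigational Product administration q" is marked at all 13 visits, including the year-end visit at Week 49. In the Year 2-4 flowchart each column serves three visits, one per year. The row "Investigational Product administration o" is marked in the first 11 visit columns. It is blank in the twelfth (Visits 25, 37 and 49; Weeks 97, 145 and 193; Days 673, 1009 and 1345) and in the Early Withdrawal column. Footnote o to that row provides for an omitted dose only when a late visit cannot be recovered: "If the subject cannot return in this timeframe, the dose should be missed".

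**The concern.** One cell governs three visits that do not have the same status. Week 193 is the last visit listed, so leaving it undosed is reasonable. Weeks 97 and 145 are followed four weeks later by dosed visits at Weeks 101 and 149, so treatment is continuing. The likely cause is that a blank meant for the final visit was applied to a column that also carries two mid-study visits.

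A site cannot satisfy both parts of the protocol. If it infuses at Week 97 it departs from the flowchart; if it does not, it departs from Sections 1.4, 3.2 and 5. At stake is an 8-week interval at two points in a long-term dosing study whose 4-week interval is justified by target coverage.

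**Working it through.** **Inputs.** Study days come from the two flowchart headers and the marks from the two study-drug rows. The intended interval is 4 weeks, or 28 days (Section 1.4).

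**Step 1: doses as the flowcharts are printed.** Number of doses in a run = (last day − first day)/28 + 1.

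| Run | First to last dosed day | Doses |
|---|---|---|
| Year 1 | 1 to 337 | 336/28 + 1 = 13 |
| Year 2 | 365 to 645 | 280/28 + 1 = 11 |
| Year 3 | 701 to 981 | 280/28 + 1 = 11 |
| Year 4 | 1037 to 1317 | 280/28 + 1 = 11 |
| Total | | 13 + 11 + 11 + 11 = 46 |

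**Step 2: intervals between runs.**

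- Year 1 to Year 2: 365 − 337 = 28 days.
- Year 2 to Year 3: 701 − 645 = 56 days (Week 93 to Week 101).
- Year 3 to Year 4: 1037 − 981 = 56 days (Week 141 to Week 149).

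The first junction keeps the interval because Week 49 is dosed. The other two double it because Weeks 97 and 145 are not.

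**Step 3: add Days 673 and 1009 (Weeks 97 and 145).**

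- 673 − 645 = 28 and 701 − 673 = 28.
- 1009 − 981 = 28 and 1037 − 1009 = 28.
- Total 46 + 2 = 48 doses, the last at Week 189 (Day 1317), with every interval 28 days.

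If Week 193 (Day 1345) were dosed too, the total would be 49, still all 28 days apart.

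**Step 4: size.** The two omitted infusions are 2/48 = 4.2% of the full course (2/49 = 4.1% if Week 193 is dosed). A boy who leaves before Week 97 loses none. One who continues to Week 101 but leaves before Week 145 loses one. One who continues to Week 149 loses two. The protocol does not say how many are expected to reach each point.

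**Step 5: do other entries suggest a planned pause?** None does. The blank column has a PK sample, which footnote p says is drawn before dosing, and infusion-site monitoring runs through it. This gives only slight support to a dose having been intended, because the Early Withdrawal column carries a PK mark as well.

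**The case against.** The strongest objection is legibility. The finding rests on one blank cell in a table read by a program, and other marks in the same flowchart look displaced. Immunogenicity falls at Week 69 while PK falls at Week 73, and Section 7.1 names Week 73, not Week 69, as the larger blood draw (22 mL). That the dosing row has the right number of cells does not settle it, since the immunogenicity row has the right number too. A lost mark cannot be excluded without the source page, and this lowers confidence. It does not remove the point. The suspect marks look shifted sideways, whereas this row has 11 consecutive marks followed by blanks, so a twelfth mark would have to have been lost outright. The liver MRI, DXA and PK rows in the same block do fill the twelfth column.

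It can also be said that the text states the regimen clearly, that drug is assigned through the IRT (Section 5.1), and that infusions are recorded (Section 5.5). All of that stands. It limits the practical effect and is why the point is minor.

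A reader might infer that the blank leaves the 84-day SAE reporting period undefined. The documents do not support this. Section 8.2 counts from each boy's actual last infusion, which is recorded, and the blank itself reads as no dose at Week 193. A reader might also infer that boys will in fact miss doses or lose target coverage. The protocol does not show how the IRT dosing visits are configured, and it gives no figure for coverage at 8 weeks.

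**Conclusion.** The point holds as a minor internal inconsistency, at medium confidence and subject to checking the source table. If the cell is blank in the source, the flowchart omits the Week 97 and Week 145 doses that Sections 1.4, 3.2 and 5 require: 46 infusions with two 56-day gaps, against 48 at 28-day intervals.

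The count of 48 assumes that Week 193 is an undosed final visit, as the blank suggests. The loss of two infusions applies only to boys who continue to Week 149 at sites that follow the flowchart literally. No analysis or power statement is affected: Section 9 describes the analyses as exploratory, and the sample size is capped by the parent study.

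**What to change.** Check the source table first. If the cell is blank there:

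1. Mark study drug at Weeks 97 and 145 in the Year 2-4 flowchart.
2. Add a footnote that no dose is given at Week 193, if that is the intention. The full course is then 48 infusions, all 28 days apart. If Week 193 is meant to be dosed, say so; the total is then 49.
3. Confirm that the IRT dispensing visits match the corrected row.

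The cost is one table cell and one footnote in an amendment, plus a check of the IRT configuration. If the source table already carries the mark, no change is needed.
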